4.7.9 Previous and Concomitant Medication

Previous and concomitant medications are non-study medications. Different from the description in the Clinical Study Protocol, which describes that the non-study medications will be coded using the World Health Organization (WHO) Drug Dictionary, the previous and concomitant medication will be coded using the Genentech (GNE) drug dictionary. This is a proprietary Roche Dictionary which is used to code concomitant medications in the Trial Management System (TMS) coding tool. The Standardized Medication Name (CMDECOD), which is the medication generic or combination generic as defined by the Drug Thesaurus (proprietary Genentech/Roche dictionary), and the Medication Class (CMCLAS), which is the primary medication class as defined by the Drug Thesaurus, will be used for the analyses.

Therapies will be classified as previous or concomitant as follows:

- Previous: If the medication end date is prior to start of combination treatment,
- Concomitant: If medication is taken anytime between the start of combination treatment and the Follow-up visit.

The number and frequency of previous and concomitant medications will be given per Medication Class and Standardized Medication Name. If patients receive more than one drug within an Medication Class or Standardized Medication Name they will be counted only once for the respective Medication Class or Standardized Medication Name.

Previously administered pirfenidone will be presented separately (see Section 4.4.3). For imputation of missing or incomplete pirfenidone start or end dates please see Section 4.8.

**Pirfenidone and nintedanib — F. Hoffmann-La Roche Ltd
Statistical Analysis Plan MA29895, Version 2.0, final, 17 May 2017**

All medications will be listed. Medication that starts after the Follow-up visit will be considered as post-treatment. This medication will be identified by a flag in the data listing.

4.8 MISSING DATA

In general, missing data will not be imputed. Exceptions will be made for the data related to adverse events and concomitant medications as described below.

For adverse events, missing start or end dates will only be imputed for determination of whether the adverse event is considered to be treatment-emergent or not by using the following principles:

Incomplete or missing onset dates will be imputed to the earliest date possible (using any reliable portions of the onset date that are available and the eCFR flag on whether the event/medication occurred prior to study drug administration) following the first dose of combination treatment. Note that the onset day is considered unreliable if the month or year portions of the date are missing, and the onset month is considered unreliable if the year portion of the date is missing. If, given the completed portions of the adverse event onset date and the known first combination treatment start date, the event could not have started after the first dose of combination treatment, then the adverse event will be considered non-treatment-emergent and the onset date will be left as an incomplete date.

If the stop date is completely missing, then the event will be assumed to be ongoing and a stop date will not be imputed.

For imputation and handling of missing intensity or relationship to study medication, please see Section [4.7.3](#).

All other missing or incomplete adverse event data will be left as missing.

For concomitant medications, missing start or end dates will only be imputed for determination of whether the concomitant medication is considered to be prior, on-treatment, post-treatment. The eCRF flag 'Select if (medication) taken prior to study' will be used in addition.

For previous pirfenidone treatment, recorded in the concomitant medication eCRF, missing month and day for the start year will be imputed with July 1st of the respective year. If the day is unknown, the 15th of the respective month will be imputed. Imputations will only be used for calculation of duration of previous pirfenidone treatment. An imputation will only be applied if not artificially leading to a previous treatment period of more than 16 weeks.

4.9 VISIT WINDOWS

Visit windows will be applied to vital signs and laboratory data and the derived visits will be used in the by-visit summarizations. If multiple observations fall within the same visit window, the observation with the most extreme value will be used in the analysis, if not stated otherwise.

For presentation of vital signs, laboratory tests, exposure and pulmonary function test results, an end of treatment (EOT) visit will be defined. This will include Week 24 data for patients who completed 24 weeks of combination treatment and data from the early discontinuation visit for patients who prematurely discontinued from combination treatment.

Table 5 Visit Windows for vital signs and laboratory data

Analysis Visit [AVISITN]	Target Day	Window (Study Days)
Baseline [0]	1	Last valid assessment prior to start of combination treatment
Week 1 [1] – lab data only	7	2 to 10
Week 2 [2]	14	11 to 17 (2 to 21 vital signs)
Week 3 [3] – lab data only	21	18 to 24
Week 4 [4]	28	25 to 42 (22 to 42 vital signs)
Week 8 [8]	56	43 to 70
Week 12 [12]	84	71 to 98
Week 16 [16]	112	99 to 126
Week 20 [20]	140	127 to 154
Week 24 [24]	168	155 to 174
Early discontinuation [25]	Not applicable	As occurred
End of treatment (EOT) [26]	Not applicable	As occurred
Follow-up [28]	Combination treatment end date + 28	As occurred

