Appendix 2 Schedule of Assessments

If	Study Period																Follow-up	Early d/c
	W/O [a]	Screening [a]	Combination Treatment															
			Visit Window, ± 3 d				Visit Window, ± 7 d										Refer to foot note for timing [b]	ASAP ≤ 7 d after decision to d/c nintedanib [c]
Study Day:	-50 to -22	-21 to -1	1 (BL)	7	14	21	28	42	56	70	84	98	112	126	140	168		
Study Week:				1	2	3	4	6	8	10	12	14	16	18	20	24		
Type of Contact:	O	O	O	P	O	P	O	P	O	P	O	P	O	P	O	O	O	O
Assessment																		
Informed consent [d]	X	X																
Complete medical history [e]	X	X																
Directed medical history [f]			X	X	X	X	X	X	X	X	X	X	X	X	X	X	X	X
Pirfenidone treatment history	X	X [g]	X [h]															
Document IPF diagnosis		X																

If	Study Period																Follow-up	Early d/c
	W/O [a]	Screening [a]	Combination Treatment															
				Visit Window, ± 3 d				Visit Window, ± 7 d								Refer to foot note for timing [b]	ASAP ≤ 7 d after decision to d/c nintedanib [c]	
Study Day:	-50 to -22	-21 to -1	1 (BL)	7	14	21	28	42	56	70	84	98	112	126	140			168
Study Week:				1	2	3	4	6	8	10	12	14	16	18	20	24		
Type of Contact:	O	O	O	P	O	P	O	P	O	P	O	P	O	P	O	O	O	O
Assessment																		
Complete physical examination, including vital signs [j]		X	X		X		X		X		X		X		X	X	X	X
Body weight (kg)		X	X		X		X		X		X		X		X	X	X	X
Height (cm)		X																
12-lead ECG [j]		X	X													X	X	X
Spirometry (FVC), and DLco [k]		X	X								X					X		X
Spirometry (FEV1) [k]		X	X															
Hematology, serum chemistry [l], CRP		X	X [m]	X [m]	X [m]	X [m]	X		X		X		X		X	X	X	X

If	Study Period																Follow-up	Early d/c
	W/O [a]	Screening [a]	Combination Treatment															
				Visit Window, ± 3 d				Visit Window, ± 7 d								Refer to foot note for timing [b]	ASAP ≤ 7 d after decision to d/c nintedanib [c]	
Study Day:	-50 to -22	-21 to -1	1 (BL)	7	14	21	28	42	56	70	84	98	112	126	140			168
Study Week:				1	2	3	4	6	8	10	12	14	16	18	20	24		
Type of Contact:	O	O	O	P	O	P	O	P	O	P	O	P	O	P	O	O	O	
Assessment																		
Urine pregnancy test [n]							X [r]		X [r]		X [r]		X [r]		X [r]	X [r]		
Serum pregnancy test [n]		X	X													X	X	X
Biomarker sample collection [o]			X				X									X		X
Review patient diary			X		X		X		X		X		X		X	X	X	X
Review AEs [p]			X	X	X	X	X	X	X	X	X	X	X	X	X	X	X	X
Review pirfenidone dosing adherence [p]			X	X	X	X	X	X	X	X	X	X	X	X	X	X		X

If	Study Period																Follow-up	Early d/c

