4.2.1 Study Days

Study day is defined as the number of days since combination treatment start date, and is calculated as:

- For assessments on or after the day of start of combination treatment:
Study day = Assessment date – Date of start of combination treatment + 1.
- For assessments before the day of start of combination treatment:
Study day = Assessment date – Date of start of combination treatment

The day of the first dose of combination treatment is defined as Day 1.

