4.7.7 Vital Signs

Vital signs, body weight and body temperature assessments will be assigned to visit windows as per Section 4.9. Descriptive statistics will be used to summarize vital signs data at baseline, at each scheduled post-baseline visit, and for the absolute change from baseline to each scheduled post-baseline visit. Line graphs for systolic and diastolic blood pressure will be provided. The body mass index (BMI) will only be calculated for the BMI at baseline and presented with the demographic data.

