4.7.8 ECG

QTcF values will be assigned to the following intervals: < 500 ms, 500–550 ms, and > 550 ms. Numbers and proportions of patients with their maximum QTcF interval category will be summarized at Baseline, Week 24 or early discontinuation, EOT and Follow-up. Absolute changes from the Baseline to each post-baseline visit in QTcF values will be categorized to ≤ 30 ms, 31–60 ms, and > 60 ms. Numbers and proportions of patients in each category will be presented for each post-baseline visit. Planned visits will be used for presentations.

At each visit, the ECG result is to be assessed as being normal, abnormal - not clinically significant, abnormal - clinically significant, or unable to evaluate. Changes from baseline to each post-baseline visit will be presented showing numbers and proportions of patients in each combination of categories.

Descriptive statistics for heart rate and changes from baseline for each visit will be presented.

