- Patients taking prohibited medications enter Washout; if prohibited medication must be tapered, patient must be off that medication 28 days before start of Screening. Other patients directly enter Screening.
- For patients who complete 24 weeks of study treatment, visit should occur 28–35 days after completion of combination treatment. For patients who prematurely discontinue study treatment or have a treatment interruption of ≥ 28 consecutive days, visit should occur 28–35 days after decision to discontinue nintedanib.
- If a patient cannot return in ≤ 7 days, study center is to call patient to review medical history and to send laboratory kit and shipping supplies to patient so that blood samples can be drawn at another study center, commercial laboratory or by home nursing agency; Early Discontinuation Visit should then be scheduled as soon as possible.
- Written informed consent must be obtained before any study-mandated assessment or procedure, including tapering and/or discontinuing prohibited medication. If written informed consent was not obtained at Washout, it must be obtained at start of Screening.
- Including systems review, and review of concomitant medications, events in 28 days before start of Screening, and historical data (including prior high-resolution computed tomography scans, pulmonary function tests, and surgical lung biopsy data, if available). If complete medical

Pirfenidone and nintedanib — F. Hoffmann-La Roche Ltd
Statistical Analysis Plan MA29895, Version 2.0, final, 17 May 2017

history was obtained during Washout, during Screening the list of concomitant medications and medical history should be updated with changes since patient signed informed consent form.

- f. Includes AEs, concomitant medications, dosing adherence, hospitalizations, inquiry regarding compliance with protocol requirements for contraceptive use and avoiding tobacco products, and inquiry regarding whether patient is aware of being pregnant.
- g. At start of Screening, patient must have been on pirfenidone for ≥ 16 weeks and on stable dose (1602–2403 mg/d) for ≥ 28 days; dose must be expected to remain in that range throughout study. Treatment interruptions > 7 days are not permitted in the 28 days before start of Screening.
- h. At Baseline Visit, patient must have been at least approximately 80% adherent to pirfenidone dosing regimen since Screening Visit.
- i. Resting BP and HR, respiratory rate, body temperature.

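### Table 5 of the SAP closes the Week 24 laboratory and vital-sign window on Day 174, one day before the schedule's own limit of Day 175

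*SAP*

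**What the plan says.** Table 5 in Section 4.9 gives the study-day window for each analysis visit. Its Week 24 row is "Week 24 [24] 168 155 to 174", the same in SAP Versions 1.0 and 2.0. The derived visits, not the nominal ones, feed the by-visit summaries. Section 4.7.7 confirms this for vital signs: "Vital signs, body weight and body temperature assessments will be assigned to visit windows as per Section 4.9". Section 4.7.6 does the same for laboratory data, unscheduled visits included.

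Study days follow Section 4.2.1: "Study day = Assessment date – Date of start of combination treatment + 1" for assessments on or after the start date, so the day of first combination dosing is Day 1. The schedule in Appendix 2 also starts at Day 1 and lists Week 24 as Day 168. Its header for the later treatment visits reads "Visit Window, ± 7 d".

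Two other timing entries stand at the right of that header. One refers to footnote b, which concerns the Follow-up visit: "For patients who complete 24 weeks of study treatment, visit should occur 28–35 days after completion of combination treatment". The other gives the timing of the Early Discontinuation Visit.

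For ECG, Section 4.7.8 uses a different basis: "Planned visits will be used for presentations".

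**The concern.** The SAP contains two windows for one visit, and they do not agree. The schedule lets the site see the patient up to Day 175, while the analysis table stops at Day 174. A programmer who follows Table 5 exactly finds no numbered visit for a Day 175 value, although the site kept to the schedule.

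At stake is the Week 24 row of the by-visit laboratory and vital-sign tables: descriptive statistics, change from baseline, and the Grade 3 and 4 laboratory counts shown over time. For the same patient on the same day, the ECG table would show a Week 24 result. Denominators at the last on-treatment visit could then differ between safety tables for a reason unrelated to missing data.

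**Working it through.** **Inputs.** Targets and upper limits come from Table 5 (Section 4.9). Tolerances come from the schedule header (Appendix 2). The day scale comes from Section 4.2.1.

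**Step 1: permitted days for Week 24.** Lower limit 168 − 7 = 161; upper limit 168 + 7 = 175. That is 175 − 161 + 1 = 15 days.

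**Step 2: days covered by Table 5.** The window is Days 155 to 174. Its overlap with Days 161 to 175 is Days 161 to 174, or 14 days. Day 175 is not covered and lies in no other numbered window.

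**Step 3: the other rows.** Upper limit minus target, set against the tolerance:

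| Visit | Target | Upper limit | Days past target | Tolerance | Shortfall |
|---|---|---|---|---|---|
| Week 1 (laboratory) | 7 | 10 | 3 | 3 | 0 |
| Week 2 | 14 | 17 (vital signs 21) | 3 (7) | 3 | 0 |
| Week 3 (laboratory) | 21 | 24 | 3 | 3 | 0 |
| Week 4 | 28 | 42 | 14 | 3 or 7 | 0 |
| Week 8 | 56 | 70 | 14 | 7 | 0 |
| Week 12 | 84 | 98 | 14 | 7 | 0 |
| Week 16 | 112 | 126 | 14 | 7 | 0 |
| Week 20 | 140 | 154 | 14 | 7 | 0 |
| Week 24 | 168 | 174 | 6 | 7 | 1 |

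The copies of the header disagree on whether Day 28 has a tolerance of 3 or 7 days. Week 4 reaches 14 days past target, so its upper limit suffices either way. Only upper limits are compared here.

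**Step 4: can Day 174 be reproduced?**
- Target plus tolerance: 168 + 7 = 175.
- The pattern of Weeks 4 to 20: 168 + 14 = 182.
- Midpoint between Day 168 and a Follow-up target of 168 + 28 = 196: (168 + 196) / 2 = 182.
- Twenty-four full weeks after Day 1, plus tolerance: 169 + 7 = 176.
- Elapsed days: Day 168 is 167 days after the start, and 167 + 7 = 174. On the SAP's day scale that is 174 + 1 = Day 175.

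Only the count of elapsed days gives 174, and Section 4.2.1 does not use that scale. An off-by-one slip is a plausible origin, but the SAP does not say how the limit was set.

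**Step 5: is Day 174 needed to keep Follow-up separate?** Take completion as the day of the Week 24 visit. The earliest on-schedule Follow-up for a completer is then 161 + 28 = Day 189. Day 175 is 189 − 175 = 14 days clear of it. Table 5 also assigns Follow-up as it occurred, not by a numbered study-day window.

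**The case against.** **The schedule header is damaged in the text extracted from the PDF.** Only the first copy, in Appendix 2 of Version 1.0, runs the 7-day tolerance from the Day 28 column through the Day 168 column. In the later copies, including those in Version 2.0, Day 168 is displaced and the footnote b entry stands in its place. This is a fair caution: the Version 2.0 grid as extracted does not show the point alone. But footnote b sets the timing of Follow-up and the remaining entry belongs to early discontinuation. No other timing rule is left for Day 168, so the reading from the intact copy is much the likelier one.

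**The consequence is very small.** This stands. It concerns one day, in descriptive tables, for an unknown number of patients that may be zero.

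**Three stronger readings are tempting, and the SAP does not support them.**
- A reader might infer that a Day 175 visit costs the patient completer status, because Section 4.7.1 cites Section 4.9 for the expected timing of Week 24. It does not: completion is decided by the eCRF answer, and the primary measure adds average daily dose.
- A reader might infer that the value is also lost from the end-of-treatment (EOT) summary. For that visit Section 4.9 says "This will include Week 24 data for patients who completed 24 weeks of combination treatment" and gives its window as occurred. The text does not settle whether the nominal or the windowed visit is meant, so loss cannot be asserted. This is missing detail, not an error.
- A reader might also fault the rule for repeats: "If multiple observations fall within the same visit window, the observation with the most extreme value will be used in the analysis". That is a stated and common safety convention. Using the scheduled or closest value instead would be a trade-off, not a correction. The direction left unstated for two-sided measures is a programming detail, and the CTCAE shift tables already carry one.

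**Conclusion.** The inconsistency is real and minor. Followed as written, Table 5 leaves an on-schedule Day 175 laboratory or vital-sign value out of the Week 24 by-visit row. The shortfall is exactly one day, and no other row of the table has one.

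The conclusion assumes that the 7-day tolerance applies to Day 168, which should be confirmed against the intact page of the schedule. How many patients are affected depends on how many are seen on Day 175, which the SAP cannot tell. The primary completion endpoint and the data listings stand as they are, and no hypothesis test depends on the affected tables.

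**What to change.** In Table 5, set the upper limit of the Week 24 window to at least Day 175, ending before Follow-up. Day 175 is the smallest limit that covers every permitted day. The pattern of Weeks 4 to 20 would give Day 182, which is still 189 − 182 = 7 days before a completer's earliest on-schedule Follow-up.

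The cost is one table cell and the matching line in the programming specification. No data collection, visit schedule or other analysis rule needs to change.

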4.10 INTERIM ANALYSES

Throughout the study, an external independent Data Monitoring Board (iDMC) will review individual SAE reports and laboratory toxicities. In addition, the iDMC is scheduled to review safety data and advise on study conduct at least three times during the study: when the first approximately 20 patients have completed 8 weeks of combination treatment or permanently discontinued study treatments, and when approximately 50% of the total patient group has completed 12 weeks of combination treatment or permanently discontinued study treatments, when approximately 75% of the total patient group has completed 24 weeks of combination treatment or permanently discontinued study treatments.

The iDMC may recommend that the Sponsor stop the study for safety concerns set forth in the iDMC Charter. Enrollment will continue during iDMC review of the 8-week data, unless the iDMC recommends that enrollment be paused or halted. Additional ad hoc

meetings or data review can be requested by the iDMC or Sponsor, if warranted. Additional information is provided in the iDMC Charter.

No formal interim analyses for efficacy are planned.

Appendix 1 Protocol Synopsis

PROTOCOL SYNOPSIS

TITLE: AN EXPLORATORY MULTICENTER, OPEN-LABEL, SINGLE ARM STUDY OF THE SAFETY AND TOLERABILITY OF PIRFENIDONE (ESBRIET®) IN COMBINATION WITH NINTEDANIB (OFEV®) IN PATIENTS WITH IDIOPATHIC PULMONARY FIBROSIS

PROTOCOL NUMBER: MA29895

VERSION NUMBER: 3

EUDRACT NUMBER: 2015-003280-11

IND NUMBER: 67,284

TEST PRODUCT: Pirfenidone (Esbriet®) and nintedanib (Ofev®)

PHASE: IV

INDICATION: Idiopathic Pulmonary Fibrosis

SPONSOR: F. Hoffmann-La Roche Ltd

OBJECTIVES AND ENDPOINTS

The primary objective for this study is to investigate the safety and tolerability of adding nintedanib to treatment with pirfenidone in patients with Idiopathic Pulmonary Fibrosis (IPF).

Eligible patients must be receiving chronic treatment with pirfenidone for at least 16 weeks and on a stable dose (1602–2403 mg/d) for at least 28 days. In patients eligible for this study, nintedanib will be added as an additional treatment for IPF (combination treatment) for 24 weeks.

STUDY OBJECTIVES

Primary Safety Objective

- Proportion of patients who complete 24 weeks of combination treatment on pirfenidone at a dose of 1602–2403 mg/d and nintedanib at a dose of 200–300 mg/d

Secondary Safety Objectives

Secondary Safety Objectives are:

- Proportion of patients who discontinue pirfenidone, nintedanib, or both study treatments because of adverse events before the Week 24 Visit
- Total number of patient days of combination treatment with pirfenidone at a dose of 1602–2403 mg/d and nintedanib at a dose of 200–300 mg/d
- Total number of days from the initiation of combination treatment to discontinuation of pirfenidone, nintedanib, or both study treatments
- Frequency and timing of adverse events (AE) and Serious Adverse Events (SAEs)

**Pirfenidone and nintedanib — F. Hoffmann-La Roche Ltd
Statistical Analysis Plan MA29895, Version 2.0, final, 17 May 2017**

38

prohibited medication will forgo Washout and directly enter Screening. At screening, after eligibility criteria have been met, patients may be provided pirfenidone for the study and will be instructed on proper use. In this case, patients will be instructed to stop taking their commercial pirfenidone and start taking the study provided pirfenidone.

During Screening, patients on a stable dose of pirfenidone may return for the Baseline Visit (Study Day 1) as soon eligibility has been confirmed. At this visit, they will have nintedanib added to the ongoing pirfenidone treatment. Nintedanib dosing will start at 100 mg once daily (QD) and be titrated to 150 mg BID over 15 days, as tolerated, according to the schedule provided in protocol **Error! Reference source not found.**

The Sponsor will supply pirfenidone and nintedanib for use in the study; nintedanib will be supplied in 100 mg and 150 mg capsules to facilitate temporary dose reduction if required for the management of AEs.

Combination treatment will continue through Week 24, with monitoring by office visits and telephone contacts. Blood samples will be obtained from all patients for analysis of clinical laboratory values.

Patients will be encouraged to remain on stable doses of pirfenidone (1602–2403 mg/d) and nintedanib (200–300 mg/d) throughout the combination-treatment period, unless dosing is modified to manage an AE. Patients will return to the clinic for a final Follow-up Visit 28–35 days after the completion of combination treatment.

If one or both study treatments are prematurely discontinued or interrupted for ≥ 28 consecutive days, nintedanib treatment will end as will the patient's participation in the study; whether commercial pirfenidone treatment continues will be left to the judgment of the Investigator. The patient will then return to the clinic as soon as possible (≤ 7 days after the decision to discontinue nintedanib) for an Early Discontinuation Visit.

[figure not shown]
In addition, 28–35 days after the decision to discontinue nintedanib, the patient will return for a final Follow-up Visit.

A patient diary will be used to record AEs, daily dosing adherence for both pirfenidone and nintedanib, and concomitant medication use from the screening visit to the final Follow-up Visit. Also, patients will receive a wallet card that provides important information relevant to study participation.

On completion of study participation, patients may be prescribed appropriate IPF treatment at the discretion of the treating physician.

An independent Data Monitoring Committee (iDMC) will review safety data and advise on study conduct at least three times during the study: when the first approximately 20 patients have completed 8 weeks of combination treatment or permanently discontinued study treatments, when approximately 50% of the total patient group has completed 12 weeks of combination treatment or permanently discontinued study treatments and when approximately 75% of the total patient group has completed 24 weeks of combination treatment or permanently discontinued study treatments. Additional ad hoc meetings or data reviews can be requested at any time by the iDMC or the Sponsor, if warranted.

Design of Study

NUMBER OF PATIENTS

Number of patients to be enrolled: approximately 80

TARGET POPULATION

Inclusion Criteria

Eligible patients for this study must meet the following criteria for study entry:

1. Written informed consent to participate in the study
2. Male or female, and age 40 through 80 years old at the start of Screening (inclusive).
3. At the start of Screening, on pirfenidone for at least 16 weeks and on a stable dose for at least 28 days (in this study, a stable dose will be defined as 1602-2403 mg/d); the dose must be expected to remain in that range throughout the study.
4. Documented diagnosis of IPF, per the Investigator per using the criteria of the 2011 American Thoracic Society / European Respiratory Society / Japanese Respiratory Society / Latin American Thoracic Association guidelines
5. The value from pulmonary function test results (from documented pulmonary function laboratory reports) measured at the screening visit as follows:
 - Percent predicted FVC ≥ 50%.
 - Percent predicted DLco (or carbon monoxide transfer capacity converted to DLco) ≥ 30%
6. Able to understand the importance of adherence to the study treatment regimen and the study protocol, and willing to follow all study requirements, including the concomitant medication restrictions, throughout the study.
7. For women of childbearing potential: agreement to remain abstinent (refrain from heterosexual intercourse) or use two adequate methods of contraception, including at

Pirfenidone and nintedanib — F. Hoffmann-La Roche Ltd
Statistical Analysis Plan MA29895, Version 2.0, final, 17 May 2017

41

least one method with a failure rate of < 1% per year, during the treatment period and for at least 3 months after the final Follow-up Visit.

- A woman is considered to be of childbearing potential if she is post-menarcheal, has not reached a post-menopausal state (≥ 12 continuous months of amenorrhea with no identified cause other than menopause), and has not undergone surgical sterilization (removal of ovaries and/or uterus).
 - Examples of contraceptive methods with a failure rate of < 1% per year include bilateral tubal ligation, male sterilization, established, proper use of hormonal contraceptives that inhibit ovulation, hormone-releasing intrauterine devices and copper intrauterine devices.
 - The reliability of sexual abstinence should be evaluated in relation to the duration of the clinical trial and the preferred and usual lifestyle of the patient. Periodic abstinence (e.g., calendar, ovulation, symptothermal, or post-ovulation methods) and withdrawal are not acceptable methods of contraception.
 - Barrier methods must always be supplemented with the use of a spermicide.
8. For men: agreement to remain abstinent (refrain from heterosexual intercourse) or use contraceptive measures and agreement to refrain from donating sperm, as defined below:
- With female partners of childbearing potential, men must remain abstinent or use a condom plus an additional contraceptive method that together result in a failure rate of < 1% per year during the treatment period and for at least for at least 4 months after the final Follow-up Visit. Men must refrain from donating sperm during this same period.
 - With pregnant female partners, men must remain abstinent or use a condom during the treatment period and for at least for at least 4 months after the final Follow-up Visit.
 - The reliability of sexual abstinence should be evaluated in relation to the duration of the clinical trial and the preferred and usual lifestyle of the patient. Periodic abstinence (e.g., calendar, ovulation, symptothermal, or post-ovulation methods) and withdrawal are not acceptable methods of contraception.

Exclusion Criteria

Patients who meet any of the following criteria will be excluded from study entry:

2. Clinical evidence of any active infection which according to the judgment of the investigator may interfere with study conduct, measurement of pulmonary function, or impact the course of IPF.
3. In the 28 days before the start of Screening, any new or ongoing moderate or severe adverse reaction considered by the Investigator to be related to pirfenidone, or an pirfenidone treatment interruption > 7 days for any reason.
4. Any condition that is likely to result in death in the 12 months after the start of Screening.
5. Lung transplantation anticipated in the 12 months after the start of Screening.
6. Any planned significant surgical intervention from the start of Screening through the final Follow-up Visit. This does not include minor surgical procedures (e.g., excision of a localized basal cell carcinoma).
7. Known hypersensitivity to the active substance or any excipient of either pirfenidone or nintedanib.
8. Any condition that, in the Investigator's judgment, might be significantly exacerbated by the known side effects associated with the administration of pirfenidone or nintedanib.
9. Mild (Child Pugh A), moderate (Child Pugh B) or severe (Child Pugh C) hepatic impairment.

**Pirfenidone and nintedanib — F. Hoffmann-La Roche Ltd
Statistical Analysis Plan MA29895, Version 2.0, final, 17 May 2017**

10. Severe renal impairment (creatinine clearance < 30 mL/min by the Cockcroft-Gault calculation), including end-stage renal disease requiring dialysis.
11. History or risk of gastrointestinal (GI) tract perforation.
12. History of unstable or deteriorating cardiac or pulmonary disease (other than IPF) in the 6 months before the start of Screening, including but not limited to, the following:
 - Unstable angina pectoris or myocardial infarction.
 - Congestive heart failure expected to require hospitalization during the study.
 - Uncontrolled clinically significant arrhythmias.
13. Electrocardiogram (ECG) with a heart-rate–corrected QT interval (corrected using Fridericia’s formula, QTcF) \geq 500 ms at Screening, or a family or personal history of long QT syndrome.
14. Bleeding risk: genetic predisposition to bleeding, a hemorrhagic event in the 12 months before the start of Screening, or abnormal laboratory coagulation parameters. Patients who require fibrinolysis, full-dose therapeutic anticoagulation (e.g., vitamin K antagonists, dabigatran, heparin, hirudin), high-dose antiplatelet therapy, or other therapy that may substantially increase bleeding risk are excluded.

Note: the following are permitted: prophylactic low-dose heparin or heparin flush as needed for maintaining an indwelling intravenous device (e.g., enoxaparin 4000 IU SC per day), as well as prophylactic use of antiplatelet therapy (e.g., acetylsalicylic acid up to 325 mg/d, clopidogrel at 75 mg/d, or equivalent doses of other antiplatelet therapy).

15. Use of strong CYP1A2 inhibitors (e.g., fluvoxamine, enoxacin) in the 28 days before the start of Screening.
16. Use of inhibitors of P-glycoprotein (e.g., ketoconazole, erythromycin) or CYP3A4 (e.g., ketoconazole, erythromycin) or their inducers (e.g., rifampicin, carbamazepine, phenytoin, St John’s wort) in the 28 days before the start of Screening.
17. History of alcohol or substance abuse in the 2 years before the start of Screening.
18. Use of any tobacco product in the 12 weeks before the start of Screening, or an unwillingness to abstain from their use through the final Follow-up Visit.
19. In the judgment of the Investigator, not a suitable candidate for enrollment, or unlikely or unable to comply with the requirements of this study.
20. Use of any investigational therapy in a clinical study protocol in the 28 days before the start of Screening
21. Pregnancy or lactation.
22. Hypersensitivity to peanuts.
23. Hypersensitivity to soy.

END OF STUDY AND LENGTH OF STUDY

Length of Study

The expected study length is up to 21 months

End of Study

January 2018

**Pirfenidone and nintedanib — F. Hoffmann-La Roche Ltd
Statistical Analysis Plan MA29895, Version 2.0, final, 17 May 2017**

INVESTIGATIONAL MEDICINAL PRODUCTS

PIRFENIDONE

Pirfenidone is approved in a 267 mg capsule dosage form.

The recommended dose is 801 mg (i.e., three 267 mg capsules) TID, at the same times each day, taken with food (total dose, 2403 mg/d). At the beginning of the study, patients will be on a stable pirfenidone dose, as defined in the inclusion criteria.

NINTEDANIB

Nintedanib is approved in 100 mg and 150 mg capsule dosage forms.

The recommended dose is 150 mg BID, approximately 12 hours apart, at the same times each day, taken with food (total dose, 300 mg/d). Both 100 mg and 150 mg capsules will be supplied to facilitate temporary dose reduction if required to manage AEs.

STATISTICAL METHODS

PRIMARY ANALYSIS

The analysis population will be the Safety Population. It will consist of all patients who received at least one dose of nintedanib or pirfenidone at the Baseline Visit (Day 1).

AEs will be coded to a preferred term and system organ class using the Medical Dictionary for Regulatory Activities (MedDRA). Laboratory abnormalities will be graded using the Common Terminology Criteria for Adverse Events (CTCAE). Prior and concomitant medications will be coded using the World Health Organization (WHO) Drug Dictionary.

Because this is a safety and tolerability study that is not designed to assess efficacy, no formal statistical hypotheses for efficacy will be assessed. The efficacy analyses will be limited to descriptive statistics.

Data summaries will be provided for baseline characteristics; patient disposition; extent of exposure; the number and proportion of patients who complete 24 weeks on pirfenidone at a dose of 1602–2403 mg/d and nintedanib at a dose of 200–300 mg/d (with 95% confidence interval [CI]); the numbers and proportions of patients with a dose reduction or a dose interruption; the number and proportion of patients who discontinued combination treatment because of a AE (with 95% CI); the total number of days on combination treatment at an pirfenidone dose of 1602–2403 mg/d and a nintedanib dose of 200–300 mg/d; the total number of days from the start of combination treatment to discontinuation of one or both study treatments; the final prescribed doses of pirfenidone and nintedanib; and the reasons for premature discontinuation of combination treatment.

AEs and SAEs leading to discontinuation will be summarized by incidence, severity, seriousness, and relationship to treatment. Additional summaries will be provided for the numbers and proportions of patients with a Major Adverse Cardiac Event (MACE), a cerebrovascular event, a bleeding event, or a thromboembolic event; the numbers and proportions of patients discontinuing combination treatment for a liver test abnormality, a GI event, or a photosensitivity reaction/rash; the numbers and proportions of patients with an emergency department visit or hospitalization; and deaths.

Observed and change values for clinical laboratory and vital signs data will be summarized. Grade 3 and 4 laboratory abnormalities will be summarized by CTCAE grade, and shift tables by CTCAE grade will be provided.

**Pirfenidone and nintedanib — F. Hoffmann-La Roche Ltd
Statistical Analysis Plan MA29895, Version 2.0, final, 17 May 2017**

ECG data will be summarized, presenting the numbers and proportions of patients with a maximum QTcF interval < 500 ms, 500–550 ms, and > 550 ms; with a maximum change from the baseline QTcF interval of ≤ 30 ms, 31–60 ms, and > 60 ms; and with ECG changes considered by the Investigator to be clinically significant.

DETERMINATION OF SAMPLE SIZE

A sample size of approximately 80 patients was selected based on the AE discontinuation rates after one year observed in the randomized Phase 3 pirfenidone studies and the randomized Phase 2 and 3 nintedanib studies (pirfenidone 14.6%, nintedanib 21%; per the 2014 US labels). Given that for pirfenidone the discontinuation rate after 24 weeks was 6%-8% in studies PIPF-004 and PIPF-006 it is a reasonable assumption that the nintedanib discontinuation rate was around 10% - 11%. As in this study of combination treatment, it is possible that the addition of nintedanib to ongoing pirfenidone treatment could increase the proportion of patients who discontinue because of an AE, given the overlap in the GI and hepatic effects of the two medications.

Assuming 85% of the patients complete 24 weeks of combination treatment, a sample size of 80 patients would be expected to yield an actual completion rate of 77.2% to 92.8% using a 95% CI

Number of Patients who completed 24 weeks	Proportion of Patients who completed 24 weeks	Lower Bound of 95% CI	Upper Bound of 95% CI
76	95.0%	90.2%	99.8%
72	90.0%	84.4%	96.6%
68	85.0%	77.2%	92.8%
64	80.0%	71.2%	88.8%
60	75.0%	65.5%	84.5%

CI = confidence interval

